### 10.2 Data Analysis Plans

#### 10.2.1 Primary Analysis

This is a prospective study to assess the diagnostic performance of the newly developed device. The **primary outcome of interest is the sensitivity and specificity of the acoustic angiography device as compared to b-mode ultrasound**. The sensitivity and specificity can be estimated non-parametrically as the proportion of the lesions which are distinguished as malignant versus non-malignant compared to the reference. This estimate will be calculated for each reader then averaged over all the readers. The standard error of the average sensitivity and specificity estimate will be calculated using the bootstrap method, where each patient is treated as independent unit with 5 ratings. The confidence interval of the final estimate will be provided using the normality assumption.

Furthermore, we will estimate the sensitivity and specificity of the b-mode ultrasound in this study and compare it with the sensitivity and specificity estimate of the acoustic angiography device using the bootstrap approach and the confidence interval of their differences will be provided using the normality assumption.

Malignancy scores of +1 and +2 will be considered malignant. Scores of -2, -1, and 0 will be considered not malignant. The confidence of malignancy will be used independently

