### 1.2 Traditional Breast Cancer Screening and Diagnosis

Breast cancer is the most common cancer type among women. Approximately 10% of women in the United States develop breast cancer during their lifetime and 30% to 40% of these patients will die from it.[33, 34] Mammography is an effective tool for the early detection of breast cancer in the majority of women.[35] However, for women with dense breast tissue (considered an independent risk factor for breast cancer) and younger women, mammography performs poorly due to lower sensitivity and specificity in these groups.[37] For young women with heritable mutations who wish to begin screening at a younger age, these limitations are especially problematic.[38] Additionally, mammography is less sensitive in women who have undergone breast augmentation. Given these limitations, most of these women may undergo additional imaging with breast ultrasound or Magnetic Resonance Imaging (MRI).

MRI is time consuming, extraordinarily costly, and has limited availability, especially among rural and underserved populations. Another screening option, breast ultrasound (without contrast), is widely used when additional imaging beyond mammogram is required due to its real-time imaging

capability (>30 images per second), portability, safety (does not involve radiation), and relatively low cost compared to breast MRI. Unfortunately, while breast ultrasound is highly sensitive (96%), it is less specific (70%), resulting in a high false positive rate. This results in unnecessary biopsies with associated complications, additional follow-up and negative psychosocial impacts on patients, e.g., significant anxiety. A significant clinical need exists to improve breast ultrasound sensitivity and specificity.

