### 10.1 Sample Size and Accrual

Per the revision in increased Perflutren dose, we have updated our sample size statistics as follows.

For power calculation, the null hypothesis is that the specificity of acoustic angiography system is the same as the standard of care (b-mode ultrasound), which is assumed to be 70%. (We will determine the specificity of b-mode ultrasound during the trial to confirm that the 70% represents the specificity in the hands of UNC radiologists) Under the alternative, we expect that the specificity of the new device is at least 90%. The specificities are measured relative to pathological diagnosis as the reference standard. With 60 lesions and 5 readers, where we anticipate that roughly half will be malignant, assuming the correlation from the same patient to be 0.5 and the readers to read different patients independently, the power to see specificity at least larger than 90% is 98% at the significance level 0.05 using one-side test. With 50 lesions (half are benign), the power to see specificity of 90% is >96%; with 25 lesions (about 13 are benign), this power becomes 72%. The power to reject the null hypothesis is 98%. Although we will study both sensitivity and specificity, our power calculation is based on specificity, which is the primary interest.

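### The normal-approximation intervals for each modality's own sensitivity and specificity are too short near 100%: at the expected device specificity of 90%, a nominal 95% interval covers about 89%

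*Combined protocol and SAP*

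**What the plan says.** Section 10.2.1 fixes the whole procedure. The estimator is a per-reader proportion: "This estimate will be calculated for each reader then averaged over all the readers". The standard error is "calculated using the bootstrap method, where each patient is treated as independent unit with 5 ratings". The interval for each modality follows: "The confidence interval of the final estimate will be provided using the normality assumption". For the comparison with b-mode, "the confidence interval of their differences will be provided using the normality assumption".

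The section names no transformation, no percentile, score or exact alternative, no confidence level, and no rule for the case where every rating is correct and the bootstrap standard error is zero.

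Section 10.1 supplies the planning values: 60 lesions with about half malignant, 5 readers, b-mode specificity 70%, and "assuming the correlation from the same patient to be 0.5". For the device, "Under the alternative, we expect that the specificity of the new device is at least 90"%. Two smaller scenarios are also given: 50 lesions (25 benign) and a third, "with 25 lesions (about 13 are benign), this power becomes 72"%. No planning value is given for sensitivity. Section 1.2 quotes 96% for conventional breast ultrasound, as background only.

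**The concern.** An estimate plus or minus z standard errors needs a roughly symmetric estimate whose standard error does not depend on the estimate. Neither holds for a proportion near 100% based on about 30 patients. When chance pushes the estimate up, the estimated standard error falls with it, so the interval is short exactly when it sits too high. The lower limit, which tells the reader how poor the device might be, is then too optimistic.

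Section 10.1 treats specificity as the measure that matters most and expects it to be at least 90%, so the problem arises at the planning value. Values above 90% are also within that expectation, and the problem is worse there. Cutting the upper limit off at 100% does not help, because the misses are at the lower limit.

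**Working it through.** **1. Check that the model is the plan's own.** Five ratings per lesion with correlation 0.5 give a design effect of 1 + 4 × 0.5 = 3. The effective sample size is 5 × (benign lesions) / 3, that is 50, 41.7 and 21.7 for 30, 25 and 13 benign lesions. For a one-sided 0.05 test of 70% against 90%,

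power = Φ[(0.20 − 1.645 √(0.7 × 0.3 / n_eff)) / √(0.9 × 0.1 / n_eff)].

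With n_eff = 50: (0.20 − 1.645 × 0.0648) / 0.0424 ≈ 2.20, power 98.6%. The other two give 96.3% and 72.3%. Section 10.1 states 98%, above 96%, and 72%, so its figures are reproduced.

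**2. Standard error of the reader-averaged estimate.** With 30 lesions the variance is p(1 − p) × 3 / (5 × 30) = p(1 − p)/50. The standard error is 0.0648 at 70%, 0.0424 at 90% and 0.0277 at 96%.

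**3. Coverage of the planned interval.** Assumptions: nominal 95%; beta-binomial ratings, 5 per lesion, correlation 0.5 (carried over to sensitivity); readers fixed, as the planned bootstrap treats them; bootstrap standard error in its limiting form (SD of patient means with divisor n, over √n). Simulated coverage:

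| True value | 30 lesions | 25 lesions | 13 lesions |
|---|---|---|---|
| 70% | 93% | 93% | 90% |
| 80% | 92% | 91% | 88% |
| 85% | 91% | 90% | 86% |
| 90% | 89% | 87% | 80% |
| 95% | 81% | 78% | 63% |
| 96% | 78% | 75% | 70% |

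Coverage is not monotone at 13 lesions because the data are discrete.

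**4. Direction of the misses at 90%.**
- 30 lesions: the whole interval is above the truth in 10% of trials and below it in 0.7% (nominal 2.5% each). The upper limit exceeds 100% in 19%.
- 13 lesions: above the truth in about 20% and below in 0.6%. The upper limit exceeds 100% in 69%, and the interval has zero width in 5%.
- If sensitivity were 96% with 30 malignant lesions: the upper limit exceeds 100% in 77% of trials, and the width is zero in 6%.

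**5. Sensitivity to the assumptions.**
- Joint distribution of the ratings (90%; 30 and 13 lesions): a Gaussian copula gives 89% and 80%; a mixture of all-agree and independent reads gives 86% and 75%.
- Explicit resampling in place of the limiting standard error: 88.5–89.2% and 78.8–80.3%.
- Correlation 0.1 / 0.3 / 0.7 / 0.9 with 30 lesions: 92 / 90 / 89 / 87% at 90%; 90 / 84 / 74 / 71% at 96%; 93% throughout at 70%.
- A 90% level (matching one-sided 0.05) with 30 lesions: 88%, 84% and 75% at 70%, 90% and 96%.

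**6. Difference between modalities.** With 30 lesions and nominal 95%, coverage is 93% for 90 v 70, 94% for 70 v 70 and for 90 v 90, and 96–97% for 96 v 96. The lowest is 90–93%, for 90 v 96, depending on the correlation between modalities. With 13 lesions, 90 v 70 gives 91%.

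**The case against.** The strongest reply is that the primary outcome is the comparison with b-mode, whose interval is near nominal, and that section 10.2.1 attaches no decision to the single-modality intervals. This stands, and it limits the importance of the point. It does not make the device's own interval correct. A decision could still rest on a single-modality result, because section 10.1 sets its null at a fixed 70%. There coverage is 93%, with the whole interval above the truth in about 5% of trials against a nominal 2.5%.

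Second, enrolment is planned at 60, so the case with 13 benign lesions is a power scenario and not the design. That is right. The result to weigh is 89% with 30 lesions. At an estimate of exactly 90% with standard error 0.0424, the normal interval is 81.7–98.3% and the logit interval is 78.1–95.8%. The limits move by 2.5 to 3.6 points, and both intervals exclude 70%.

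Third, the 95% level, the joint distribution of the ratings and any sensitivity value are assumptions. This also stands, but every variant tried leaves coverage at 90% below nominal, and the alternative rating model gives a larger shortfall.

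Fourth, leaving the difference interval alone accepts 90% coverage in the 90 v 96 case. That is fair, but neither planned value of specificity is 96%; at the planned 90 v 70 the figure is 93%.

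**Conclusion.** The concern holds. At the plan's own value of 90% with 30 benign lesions, a nominal 95% interval for device specificity covers about 89%, and the misses almost all favour the device. Coverage is 87% and 80% in the two smaller scenarios of section 10.1. It drops to 81% at a true 95% with 30 lesions, which is within the stated expectation of at least 90%, and to 78% if sensitivity is near 96%. At 70% the loss is small.

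These figures rest on an assumed 95% level, the 0.5 correlation of section 10.1, and fixed readers. The exact percentages depend on the rating model; the direction does not. The primary between-modality comparison is largely unaffected. The change should be made, but the study's main comparison does not depend on it.

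**What to change.** Form each single-modality interval on the logit scale: keep the bootstrap standard error, divide it by p̂(1 − p̂), add and subtract the quantile, and back-transform. If every rating is correct, report an exact binomial lower bound based on the number of patients; at 95% this is 0.025^(1/n), or 88.4% for 30 patients and 75.3% for 13. State the confidence level. The difference interval can stay as written.

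Results with 30 lesions (the t version uses n − 1 degrees of freedom and scales the standard error by √(n/(n − 1))):

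| True value | As planned | Logit | Logit with t |
|---|---|---|---|
| 70% | 93% | 95% | 96% |
| 90% | 89% | 93% | 94% |
| 95% | 81% | 89% | 93% |
| 96% | 78% | 97% | 97% |

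The t version is preferable at the planned size because plain logit still dips to 89% at 95%.

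The cost is a short change to section 10.2.1 and a few lines of code, with no new data. Mean width at 90% with 30 lesions rises from 15.8 to 16.8 points (18.0 with t). If only 13 benign lesions were available the cost would be greater: mean width at 90% goes from 21.9 to 25.6 (30.2 with t), with coverage of about 91% for plain logit and 98% with t, which is then conservative.

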### 10.2.2 Secondary Analyses

#### Radiologist Preference

The secondary analysis will be to estimate the receiver operating characteristic (sensitivity and specificity) curve for the acoustic angiography system, with an additional aim of evaluating reader preference for specific breast lesion characteristics. Specifically, to compare the diagnostic performance, we will non-parametrically calculate the area under the ROC curve for each reader and each modality, where the ROC curve is derived using the different cut-off of the probability scores across 60 patients. We then fit a mixed effect model, where the outcomes are the estimated area under the ROC curves and the fixed effect is the dummy variable of the acoustic angiography system vs. conventional b-mode ultrasound. The readers will be treated as random effect. F-test from model fitting will be used to test whether the acoustic angiograph has a significant larger AUC than the conventional b-mode ultrasound (with significance level 0.05).

To assess the reader preference for modality for each characteristic including shape, margins and vascularity, we will fit a random effect model with only intercept and random terms for patients and readers while the outcomes are the confidence scores (-3 to +3) . By testing the intercept significantly larger than zero, we will conclude that the new modality provides more confidence for readers than the conventional one.

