#### 4.6 Reader Study

A total of five readers (radiologists trained in breast imaging) will be recruited to participate in evaluation of all imaging performed under LCCC1405.

In the reader preference study, each reader will be asked to compare the acoustic angiography case to the conventional b-mode ultrasound case to evaluate the imaging characteristics based on the BIRADS ultrasound lexicon

(<http://www.acr.org/~media/ACR/Documents/PDF/QualitySafety/Resources/BIRADS/USLexiconClass.pdf>). Specifically the relative ability to evaluate shape, margins and vascularity will be evaluated using a seven-point scale (-3 to +3) for the paired modality comparisons for each of the 60 cases.

The data collection form for the reader study portion is given in Appendix A, section 13.1.

The readers will be asked to assign a subjective malignancy score (-2 (highly not malignant) to +2 (highly malignant)) and their confidence for each lesion for each modality (0 to 100%). These will also be documented on the form in Appendix A. These scores will be used combined for a binary analysis. Malignancy scores of +1 and +2 will be considered malignant. Scores of -2, -1, and 0 will be considered not malignant. The confidence of malignancy will be used independently in the analysis.

### 5.0 Research Ultrasound Scanner: FUJIFILM VisualSonics Vevo 770

The device used for this study will be a research ultrasound scanner (FUJIFILM VisualSonics Vevo 770) and unique probes developed in conjunction with the research lab run by the founder of VisualSonics, [name]. The ultrasound probes are modifications of Vevo 770 probes (RMV716 probes), modified to house 2 single-element transducers instead of 1.

The Vevo 770 is a research ultrasound system designed for pre-clinical, high resolution imaging of small animals. It is marketed commercially by VisualSonics, Inc., a division of SonoSite, Inc., under the parent company FUJIFILM. This ultrasound system and similar models have been designated to pose no significant risk in other clinical trials by the respective IRBs or other similar regulatory agencies responsible for compliance oversight of these studies. (See section 13.1, Appendix B).

[figure not shown]
[figure not shown]

Figure 1. Device Image

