#### Overall Assessment:

##### Acoustic Angiography

Overall specimen malignancy score (-2 to +2): \_\_\_\_\_

Malignancy confidence (0-100) \_\_\_\_\_%

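### The rating behind the reader ROC curve is not defined, and the unanchored 0-100% confidence item allows two meanings that give very different AUCs

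*Combined protocol and SAP*

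**What the plan says.** Section 4.6 asks each reader, for each lesion and modality, to "assign a subjective malignancy score (-2 (highly not malignant) to +2 (highly malignant") and to give "their confidence for each lesion for each modality (0 to 100" per cent). Two later sentences in 4.6 describe the use of these ratings. The first is "These scores will be used combined for a binary analysis", followed at once by the rule that +1 and +2 count as malignant and -2, -1 and 0 as not malignant. The second is "The confidence of malignancy will be used independently in the analysis".

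Appendix A prints the second rating as "Malignancy confidence (0-100" per cent), once for each modality, with no anchors and no instruction.

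Section 10.2.1 repeats the binary rule and then says "The confidence of malignancy will be used independently", without naming the analysis in which that happens.

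Section 10.2.2 (Radiologist Preference) computes a non-parametric AUC for each reader and modality and says that the "ROC curve is derived using the different cut-off of the probability scores across 60 patients". The AUCs then enter a mixed model that compares the two modalities. Under Predicting Malignancy, the reader AUC is also the comparator for the tortuosity model.

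**The concern.** The plan does not say which recorded item is the probability score, nor whether a lesion that the reader is sure is benign should be rated near 0 or near 100 on the 0-100% item. If that item feeds the ROC curve, the answer decides whether the AUC means anything. As probability of malignancy, it ranks lesions from benign to malignant. As certainty in the call just made, it places sure-benign lesions beside sure-malignant ones, and its ranking is no longer a ranking of suspicion.

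The AUC comparison between modalities (objective 2.2.1) and the comparison of the tortuosity score with the readers (objective 2.2.4) both rest on this rating. With five readers and two modalities the mixed model has ten AUCs, so one reader with a different understanding of the item carries weight.

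**Working it through.** **Plan's own figure.** The plan states no AUC and no power for the AUC comparison, so there is none to reproduce. Its only computed design figure is the power for specificity, checked here to confirm the inputs. With 30 benign lesions, 5 readers and correlation 0.5, the effective n is 30 × 5 / (1 + 4 × 0.5) = 50. The standard error is √(0.7 × 0.3/50) = 0.0648 under the null and √(0.9 × 0.1/50) = 0.0424 under the alternative. Power is Φ[(0.20 − 1.645 × 0.0648)/0.0424] = Φ(2.20) = 98.6%, against the stated 98%.

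**Wording, side by side.**
- For probability of malignancy: the form label in Appendix A, and the term confidence of malignancy in 4.6 and 10.2.1.
- Open to confidence in the call: "and their confidence for each lesion for each modality (0 to 100" per cent) in 4.6, placed directly after a signed score that already gives the direction.
- Also for confidence in the call: the preference items on the same form use confident only for sureness about what the reader sees, and 10.2.2 calls the -3 to +3 preference ratings confidence scores.

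**Inputs for the AUC check.** From the documents: b-mode sensitivity 96% and specificity 70% (section 1.2); specificity 90% expected for acoustic angiography, and about half the lesions malignant (section 10.1). Assumed: equal-variance binormal ratings, prevalence 0.5, and a sensitivity for acoustic angiography, which the documents do not give (96% in the example, varied from 70% to 96% elsewhere). The AUC of 0.85 is illustrative.

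**Meaning 1, probability of malignancy.** AUC = Φ[(z(sens) + z(spec))/√2].
- 96/70: Φ[(1.751 + 0.524)/1.414] = 0.946.
- 96/90: Φ[(1.751 + 1.282)/1.414] = 0.984.

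**Meaning 2a, calibrated confidence in the call, used unsigned.** The rating is the posterior probability p of malignancy if the call is malignant, and 1 − p if it is benign.
- By simulation the AUC is 0.497 to 0.514 in eight sensitivity/specificity scenarios (0.514 at 96/70, 0.502 at 96/90).
- A true AUC of 0.85 becomes 0.50.
- Five-reader average with one such reader: (4 × 0.85 + 0.50)/5 = 0.78. With two: (3 × 0.85 + 2 × 0.50)/5 = 0.71.
- Restoring the sign of the call recovers the true AUC in every scenario.

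**Meaning 2b, distance from the reader's own cut, used unsigned.** By numerical integration:

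| Sens/spec | True AUC | AUC from unsigned distance |
|---|---|---|
| 96/70 | 0.946 | 0.774 |
| 96/90 | 0.984 | 0.626 |
| 90/90 | 0.965 | 0.500 |
| 80/90 | 0.933 | 0.394 |
| 70/90 | 0.899 | 0.337 |

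For b-mode at 96/70 and acoustic angiography at 96/90, the true difference is 0.984 − 0.946 = +0.038, and such a reader shows 0.626 − 0.774 = −0.148. One of five gives an average difference of (4 × 0.038 − 0.148)/5 = 0.001, so the true difference disappears. Two of five give (3 × 0.038 − 2 × 0.148)/5 = −0.036, a reversal.

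**Repair of completed forms.** Suppose the signed score is combined with the item as magnitude when the reader in fact gave probability of malignancy. A -2 lesion at 5% becomes −5 and a -1 lesion at 30% becomes −30, which reverses the order of the benign calls. With assumed score cuts at p = 0.1, 0.4, 0.6 and 0.9, this lowers a correct AUC from 0.85 to 0.80, and from 0.946 to 0.90. The five-point score alone, with the same cuts, gives 0.83 for a true 0.85.

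**The case against.** The best defence is that the item is already what it needs to be. The form that readers complete ties the percentage to malignancy, 4.6 and 10.2.1 do the same, and probability score is a fair name for such a rating. Only the first mention in 4.6 is loose. Under this meaning the AUC is valid and nothing is lost. That is the better-supported reading, and it stands. It does not show that all five readers will adopt it from an unanchored label beside a signed score.

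Some stronger readings are tempting but not supported:
- A reader might infer that the plan commits the ROC curve to the confidence item alone. Section 10.2.2 never names that item, and the five-point score is not ruled out.
- A reader might infer that the AUC must collapse to 0.5. That follows for calibrated confidence, and for equal sensitivity and specificity in the distance model. Elsewhere in that model the AUC is biased (0.34 to 0.77) rather than uninformative.
- A reader might infer that the data could not be repaired. The signed score is recorded beside the percentage on every form, and AUCs are computed reader by reader, so unusual use can be looked for.
- A reader might see a contradiction between combined and independent use. The sentence on combined use leads straight into the binary rule, so it probably means pooling score categories.

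**Conclusion.** The point holds as a defect of definition in a secondary analysis. Section 10.2.2 cannot be run without choosing a variable that the plan does not name, and the likely variable is collected in a form that allows two meanings. If all readers rate probability of malignancy, no harm follows. If one or two of five rate confidence in the call, an average AUC of 0.85 becomes about 0.78 or 0.71 under calibrated confidence. Under the distance model the modality difference can vanish or reverse.

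These sizes depend on the assumed binormal model, prevalence 0.5, the illustrative AUC of 0.85, the assumed 96% sensitivity for acoustic angiography, and the number of readers affected, which nobody can know in advance. The primary sensitivity and specificity analysis uses the cut on the signed score and is unaffected. The change should be made: how a reader used the item is hard to settle reliably afterwards and trivial to settle beforehand.

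**What to change.** Before reading starts:
- In 4.6 and on Appendix A, for both modalities, reword the item as: *Probability that this lesion is malignant: 0 = certainly benign, 50 = undecided, 100 = certainly malignant.*
- In 10.2.2, name this item as the ROC variable.
- Add an entry check that the item and the signed score agree in direction.
- In 4.6, clarify that combined use means pooling score categories for the binary cut. Keep the sentence, since it introduces that rule.

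For any forms already completed:
- First check, reader by reader and blinded to pathology, how the item was used. High values beside scores of -2 or -1 point to confidence in the call.
- Apply a pre-specified signed combination, with a stated rule for a score of 0, only to readers who used the item that way. Alternatively, use the five-point score for the ROC curve. Do not apply the signed combination to all readers, since it damages ratings given as probabilities.

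The cost is one line on the form, a few sentences in the plan and a simple data check. Patients are not affected.

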### 2.2 Secondary Objectives

2.2.1 To compare the area under the curve (AUC) of acoustic angiography to the AUC of the b-mode ultrasound

2.2.2 To compare radiologist preference of acoustic angiography to conventional b-mode ultrasound for each lesion characteristic (shape, margins and vascularity)

2.2.3 To quantify vessel tortuosity metrics for the acoustic angiograph images, and to use these metrics to develop a model for predicting malignancy (a model-based malignancy score)

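### The AUC test for objective 2.2.1 treats only readers as random, so chance differences between modalities in the 60 shared patients are left out of its error term

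*Combined protocol and SAP*

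**What the plan says.** Objective 2.2.1 is "To compare the area under the curve (AUC) of acoustic angiography to the AUC of the b-mode ultrasound". The method is in section 10.2.2, under the Radiologist Preference subheading. An empirical AUC is calculated for each reader and modality over the 60 patients. Then: "We then fit a mixed effect model, where the outcomes are the estimated area under the ROC curves". Modality is the fixed effect and reader the only random effect named. The decision rule is "F-test from model fitting will be used to test whether the acoustic angiograph has a significant larger AUC than the conventional b-mode ultrasound", at level 0.05.

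The design is fully crossed. Section 4.6 states: "A total of five readers (radiologists trained in breast imaging) will be recruited to participate in evaluation of all imaging performed under LCCC1405".

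Elsewhere the plan does allow for patients. The primary bootstrap in section 10.2.1 is one "where each patient is treated as independent unit with 5 ratings". The preference analysis, in the paragraph after the AUC test, is a "random effect model with only intercept and random terms for patients and readers". No section gives the AUC test a patient term, a covariance between the AUCs, or patient resampling.

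**The concern.** Only ten numbers enter the model: five readers times two modalities. The F-test for modality then has 1 and 4 degrees of freedom and equals a paired t-test on the five within-reader differences. Its error term is the spread of those differences between readers.

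Each AUC also carries error from the particular 60 lesions sampled. The part that is the same in both modalities cancels in the difference. The part specific to one modality does not cancel, and all five readers share it because they read the same cases. It moves the mean difference but leaves the between-reader spread alone, so the test cannot see it. A chance feature of these 60 lesions, repeated by five readers, can then be reported as a significant AUC difference. This is the only planned modality test for objective 2.2.1.

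**Working it through.** **The plan's figures.** The AUC test has a nominal level of 0.05 and no power calculation. The one usable correlation is in section 10.1, given for the specificity power: "assuming the correlation from the same patient to be 0.5". Reading it as the correlation between readers on the same patient reproduces that calculation:

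- Effective n = 30 × 5 / (1 + 4 × 0.5) = 50.
- Power = Φ[(0.20 − 1.645 × √(0.21/50)) / √(0.09/50)] = 98.6% (plan: 98%).
- With 25 benign lesions it is 96.3% (plan: >96%); with 13 it is 72.3% (plan: 72%).

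So 0.5 is the plan's own inter-reader correlation, but for binary calls. Using it for AUC ratings is an assumption.

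**Theory.** Let the AUC errors have correlation r2 (same modality, different readers), r1 (different modalities, same reader) and r3 (both different). With no reader-by-modality variance and five readers, under the null:

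E[MS modality] / E[MS modality × reader] = [1 − r1 + 4(r2 − r3)] / [1 − r1 − (r2 − r3)]

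A valid test needs a ratio of 1, which requires r2 = r3. For r2 = 0.5 and r1 = r3 = 0.25 the ratio is (0.75 + 1.00)/(0.75 − 0.25) = 3.5. The approximate rejection rate is P(|t4| > 2.776/√3.5) = 21.2%.

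**Simulation.** Inputs: 30 malignant and 30 benign lesions (section 10.1 expects roughly half malignant), five readers, normal latent ratings, true AUC 0.85 in both modalities, inter-reader correlation 0.5, 5,000 runs per setting. The correlations are set on the rating scale. All rates are two-sided at a nominal 5%.

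| Cross-modality correlation | Ratio | Theory | Planned test, no reader-by-modality variance | Planned test, between-reader AUC SD about 0.05 per modality | Obuchowski-Rockette/Hillis, no reader-by-modality variance |
|---|---|---|---|---|---|
| 0 | 6.0 | 32.0% | 27.2% | 13.3% | 5.6% |
| 0.25 | 3.5 | 21.2% | 18.0% | 10.3% | 4.5% |
| 0.375 | 2.25 | 13.8% | 12.5% | 8.0% | 5.4% |
| 0.45 | 1.5 | 8.6% | 7.6% | 5.6% | 5.2% |
| 0.5 | 1.0 | 5.0% | 5.3% | 4.9% (3,000 runs) | 4.7% |

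Theory and simulation differ because the theory applies the same values to AUC errors and the simulation applies them to ratings. At correlation 0.25 the true SD of the mean AUC difference is 0.040, against a mean model SE of 0.022. The squared ratio, (0.040/0.022)² = 3.3, agrees with the 3.5 above.

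**Sensitivity.**

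- Inter-reader correlation 0.3: 15.5%, 11.0% and 4.7% at cross-modality correlation 0, 0.15 and 0.3.
- Inter-reader correlation 0.7: 43.1%, 30.0% and 4.6% at 0, 0.35 and 0.7.
- True AUC 0.75 or 0.92 at cross-modality correlation 0.25: 20.0% or 17.8%.
- A differently parameterised simulation (27 settings, 4,000 runs each), which splits the patient variance into common and modality-specific parts: the planned test rejected 3.9% to 30.6%, and Obuchowski-Rockette/Hillis 3.8% to 6.2%. With no modality-specific patient variance the planned test stayed at 3.9% to 5.3%.
- If the software sets a negative reader variance to zero, the test is no longer exactly the paired t-test. In those settings this raised the rate by at most 1.4 percentage points.

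**One-sided reading.** The text tests for a larger AUC. As a one-sided 5% test without reader-by-modality variance, the rates are 19.1%, 13.8%, 10.4%, 7.3% and 4.8% down the table rows. Under the two-sided F-test, false findings in favour of acoustic angiography alone are 13.8%, 8.6%, 6.3%, 4.3% and 2.4%, against a nominal 2.5%.

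**The case against.** The strongest reply concerns size. The documents give neither the cross-modality correlation nor the reader-by-modality variance, and 0.5 is stated for another endpoint on another scale. Both modalities image the same lesion and are scored on one form, so zero correlation is an outer bound. If readers differ strongly in how much they gain from the new modality, the excess shrinks: with the largest reader-by-modality variance tried, the rate was only 7.6% even with substantial modality-specific patient variance. Two-sided rates also count errors that favour b-mode. All of this stands. It limits what can be said about size, but not about direction: any modality-specific patient variance pushes the level above nominal, and the one-sided reading is inflated too. Identical patient effects are also not to be expected, since section 1.3.1 describes one technique as showing vessel shape and the other as locating the lesion.

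A second reply is that the reader-only test is valid conditional on these 60 lesions. That is true, but the plan does not limit its conclusion to them, and section 10.2.1 describes the study as assessing the device's diagnostic performance.

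Third, this is one secondary test, and the sample size rests on specificity. That bears on priority and does not remove the fault.

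**Conclusion.** The concern holds. As written, the AUC test omits patient-by-modality error and keeps its 5% level only if patient effects are the same in both modalities. The omission is certain from the text. Its size is conditional: with inter-reader correlation 0.5 and AUC 0.85, about 5% to 27% two-sided without reader-by-modality variance, and about 5% to 14% with a between-reader AUC SD near 0.05 per modality. The primary comparison resamples patients and does not share this omission. The point should be fixed before analysis, but no primary conclusion depends on it.

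**What to change.** Replace the ten-value model in section 10.2.2 with a multi-reader multi-case analysis in which readers and patients are both random. The Obuchowski-Rockette model does this. With r readers, F = MS modality / {MS modality × reader + max[r(Cov2 − Cov3), 0]}, where Cov2 and Cov3 are the between-reader AUC covariances within and across modalities, estimated over patients by jackknife, bootstrap or DeLong. Use Hillis denominator degrees of freedom.

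Do not simply carry over the patient-only bootstrap of section 10.2.1. It makes readers fixed, whereas section 10.2.2 treats them as random. With the reader-by-modality variance above it rejected 13.4% and 18.4% at cross-modality correlation 0.25 and 0.45. A bootstrap over both patients and readers with a normal interval keeps the intended target but is conservative with five readers (0.5% to 3.2%).

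Also state whether the test is one- or two-sided: an F-test is two-sided, while the text asks for a larger AUC.

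The cost is SAP wording and standard software, with no new data. The result will usually be less favourable. At cross-modality correlation 0.25 the mean AUC difference needed for significance rises from 0.061 to 0.082. At 0.5 it is 0.060 under both methods.
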